3.3 Exploratory Objectives

- To investigate the association of PD-L1 protein expression by pretreatment tumor with response to treatment.
- To investigate the association of regulatory T cell (Treg) frequency and Treg to effector T cell (Teff) ratios in peripheral blood and tumor tissue with response to therapy.
- To investigate the association of *de novo* serological and cellular responses against the ubiquitous RCC tumor antigen 5T4 with response to therapy.
- To investigate the association of tumor infiltrating lymphocyte (TIL) repertoire clonality with response to therapy and to assess the detection of dominant TIL clones within peripheral blood over time in responding patients.
- To investigate the association of whole genome copy number alterations measured on pretreatment archived, formalin fixed, paraffin embedded (FFPE) tumor with response to therapy.

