4.2.2 Hypothesis for Combination Therapy

The immune checkpoint receptor PD-1 and associated ligand PD-L1 may represent a dominant mechanism for RCC resistance and escape from immune surveillance and from anti-tumor effects mediated by IL-2. Targeting PD-1 with the blocking mAb pembrolizumab in combination with IL-2 will result in a higher frequency and/or greater depth of anti-tumor effects in comparison to the historical experience with anti-PD1 or IL-2 monotherapy in untreated or in treatment-refractory patients.

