4.2.4.3.5 The Association of Chromosomal Copy Number Alterations with Response to Therapy

Gain-of-function oncogene mutations are rarely identified in whole-exome or whole-genome sequencing derived data sets for ccRCC tumors [60]. As a consequence, targeted gene-sequencing based diagnostic panels have not made inroads into the clinical management of ccRCC patients. In contrast, metastatic ccRCC tumors frequently contain large scale chromosomal abnormalities representing irreversible genetic derangements that can be readily identified by cytogenetic or array-based comparative genomic hybridization technologies [61, 62]. Deletion of 3p is detected in the majority of ccRCC tumors and spans the Von Hippel Lindau (VHL) tumor suppressor gene at 3p21. Additional common chromosomal abnormalities include gains (5q, 7) and losses (3p, 14q, 8p, 6q, 9p, 4p, and Y in males) occurring in > 10% of ccRCC tumors [61]. A subset of these chromosomal lesions (loss of 9p, 14q, and gain of 8q) represent independent poor prognostic markers for disease-specific survival [63-65].

Hypothesis: Subsets of ccRCC tumors defined by common chromosomal gains or losses will have different response rates to combination immunotherapy with IL-2 and pembrolizumab.

Until recently, cytogenetic or array-based tumor genomic analyses required fresh tumor or frozen tissue specimens respectively, for analysis. The OncoScan (Affymetrix, Santa Clara, CA) array platform is optimized for whole genome analysis of DNA isolated from formalin-fixed paraffin-embedded (FFPE) tissue. The ability to collect whole genome chromosomal CNA data retrospectively from FFPE tumor tissue now allows for directed analysis of patient cohorts receiving a common treatment to correlate genomic phenotypes with clinical outcomes. OncoScan chromosomal array analyses will be carried out on archived tumor for RCC patients treated with IL-2 and pembrolizumab and chromosomal CNAs correlated to objective response rate.

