5.0 METHODOLOGY

5.1 Entry Criteria

5.1.1 Subject Inclusion Criteria

In order to be eligible for participation in this trial, the subject must:

1. Be willing and able to provide written informed consent for the trial.
2. Be ≥ 18 years of age on day of signing informed consent.
3. Have histologic confirmation of RCC with a clear cell component.
4. Have advanced (not amenable to potentially curative surgery) or metastatic RCC.
5. May have received previous systemic treatments or regimens for metastatic RCC. Prior therapy can include checkpoint blocking antibodies targeting PD-1, PD-L1, or cytotoxic T-lymphocyte-associated antigen-4 (CTLA-4) and/or targeted agents including TKIs, mTOR inhibitors, or bevacizumab. Patients may choose to receive study treatment as their initial therapy.
6. Previously treated patients must have documented disease progression after their last line of therapy.
7. Have measurable disease based on RECIST 1.1.
8. Available tissue from an archival tissue sample or newly obtained core or excisional biopsy of a tumor lesion.
9. Have a performance status of 0 or 1 on the ECOG Performance Scale.
10. Demonstrate adequate organ function as defined in Table 2. All screening labs should be performed within 14 days of treatment initiation.

Table 2 Adequate Organ Function Laboratory Values

System	Laboratory or Study Value
Hematological	
Absolute neutrophil count (ANC)	$\geq 1,500 / \text{mcL}$
Platelets	$\geq 100,000 / \text{mcL}$
Hemoglobin	$\geq 9 \text{ g/dL}$ or $\geq 5.6 \text{ mmol/L}$
Renal	
Serum creatinine OR Measured or calculated ^a creatinine clearance (GFR can also be used in place of creatinine or CrCl)	$\leq 1.5 \times$ upper limit of normal (ULN) OR $\geq 40 \text{ mL/min}$ for subject with creatinine levels $> 1.5 \times$ institutional ULN
Hepatic	
Serum total bilirubin	$\leq 1.5 \times$ ULN OR
	Direct bilirubin \leq ULN for subjects with total bilirubin levels $> 1.5 \text{ ULN}$
AST (SGOT) and ALT (SGPT)	$\leq 2.5 \times$ ULN OR $\leq 5 \times$ ULN for subjects with liver metastases
Coagulation	
International Normalized Ratio (INR) or Prothrombin Time (PT) ^b	$\leq 1.5 \times$ ULN unless subject is receiving anticoagulant therapy as long as PT or PTT is within therapeutic range of intended use of anticoagulants
Activated Partial Thromboplastin Time (aPTT) ^b	$\leq 1.5 \times$ ULN unless subject is receiving anticoagulant therapy as long as PT or PTT is within therapeutic range of intended use of anticoagulants
Pulmonary	

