7.2.2.5 Tumor Imaging and Assessment of Disease

Tumor imaging by CT or MRI scans will be obtained at screening, at the end of each treatment course, and every 12 weeks following completion of therapy for patients who remain in Surveillance Follow-Up as specified in the Trial Flow Chart ([Section 6.0](#)). Disease status will be assessed versus baseline imaging for response category by RECIST 1.1 criteria (see Section 13.3).

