9.0 STATISTICAL ANALYSIS PLAN

9.1 Statistical Analysis Plan

The primary objective of this study is to evaluate the safety of IL-2 in combination with pembrolizumab. Statistical analysis will be descriptive for observed toxicities.

The secondary objective is to evaluate clinical outcomes (CR, PR, ORR, DCR, PFS) in comparison to historical data among advanced RCC patients treated with HD IL-2 or anti-PD1 monotherapies. The target enrollment for a conditional expansion cohort will be exploratory in nature, and no predictive statistical analysis has been applied.

Progression-free survival will be defined from the time of registration to progression or death. Patients last known to be alive and progression-free will be censored at the date of their last disease assessment. PFS will be evaluated using the method of Kaplan-Meier. Median PFS times and associated 95% confidence interval will also be calculated.

Exploratory objectives include the evaluation of the PD-1 pathway. For this objective, PD-1 pathway protein expression measures will be correlated with clinical outcomes. Specifically, the

association between pre-treatment PD-L1 expression by IHC, TIL density and T cell subset identification for CD4+, CD8+ and Treg cells, and peripheral blood analysis to quantify lymphocyte subsets including CD4+/CD8+/Treg and overall response will be compared using logistic regression. In addition, the association between end of cycle peripheral blood re-analysis to quantify lymphocyte subsets including CD4+/CD8+/Treg and PFS will be evaluated using a Cox proportional hazards model, among patients alive and progression-free at end of treatment. Similarly, the association between PD-L1 expression by IHC and TIL density and T cell subset identification for CD4+, CD8+ effector and Treg cells at the end of treatment and PFS will be evaluated among patients who do not achieve a CR but are also progression-free and the end of treatment.

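### Section 9.1 relates the pretreatment markers it names only to response, most naturally yes/no, in 12 to 15 patients; percent tumour change from the same scans is never analysed, at a cost in power that depends on an unstated correlation

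*Combined protocol and SAP*

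**What the plan says.** Section 3.3 sets exploratory objectives of the form "To investigate the association of PD-L1 protein expression by pretreatment tumor with response to treatment". For the pretreatment markers that it names (PD-L1 by IHC, TIL density, tumour T-cell subsets, blood lymphocyte subsets), section 9.1 gives one method: the marker and "overall response will be compared using logistic regression". It does not define the coding of overall response. Section 4.2.4.2 defines ORR as CR plus PR, so responder versus not is the natural reading. Cox models for PFS appear in 9.1 only for markers measured at end of cycle or end of treatment.

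Two other pretreatment markers have no method in 9.1. For copy number, section 4.2.4.3.5 plans "chromosomal CNAs correlated to objective response rate". For TIL clonality, section 4.2.4.3.4 promises a correlation with clinical outcomes and names neither outcome nor model.

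On measurement, inclusion criterion 7 reads "Have measurable disease based on RECIST 1.1", and section 7.2.2.5 schedules imaging at screening, at the end of each course and every 12 weeks in surveillance. That section then says "Disease status will be assessed versus baseline imaging for response category by RECIST 1.1 criteria". Percent change is not named as an outcome anywhere.

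Section 1.0 gives N as 12 to 15. No alpha, power or expected correlation is stated for any marker. The remark in 9.1 that "no predictive statistical analysis has been applied" concerns the conditional expansion cohort.

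**The concern.** A RECIST category rests largely on the change in target-lesion sum, so that change is available before the category is assigned. Reducing it to responder or not makes a patient just short of partial response equal to one whose tumour grew greatly, and a bare partial response equal to near-complete shrinkage. At response rates of 25% to 50%, 12 to 15 patients yield about 3 (0.25 × 12) to 7.5 (0.50 × 15) responders. Little ordering between patients is left to set against a marker.

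At stake is the chance of seeing a real association in the response-based exploratory objectives of 3.3. The plan gives no reason for using the category alone in these analyses, and choosing a scale after the data are seen would weaken any finding.

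**Working it through.** **No figure to reproduce.** The plan states no power for these analyses, so the check is a comparison under stated assumptions.

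**Inputs from the documents.** N = 12 and 15 (1.0). Response rates of 25% (phase III nivolumab study, 4.1.3), 36% (first-line pembrolizumab, clear cell cohort, 4.1.4) and 77% (pembrolizumab followed by the combination with high-dose IL-2, 4.2.1).

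**Assumptions, not in the documents.** Response rate of 50% as a further case; two-sided 5% level; one marker at a time, no multiplicity adjustment; correlation ρ between marker and shrinkage from 0.3 to 0.8.

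**Model.** Marker x is standard normal. Shrinkage is u = ρx + √(1 − ρ²)·e, with e standard normal. A patient responds if u exceeds the normal quantile z giving response rate p (z = 0.674, 0.358 and 0 for p = 25%, 36% and 50%).

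**Why the cut costs power.** The correlation of x with the yes/no outcome is ρ·φ(z)/√(p(1 − p)). At ρ = 0.6:
- p = 25%: 0.6 × 0.318/0.433 = 0.44
- p = 36%: 0.6 × 0.374/0.480 = 0.47
- p = 50%: 0.6 × 0.399/0.500 = 0.48

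**Power at ρ = 0.6.** Spearman correlation with a simulated 5% critical value, against the exact rank-sum test of x by response (20,000 replicates):

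| N | Response rate | Percent change | Responder cut | Difference (points) |
|---|---|---|---|---|
| 12 | 25% | 48.6% | 23.3% | 25.3 |
| 12 | 36% | 47.8% | 29.9% | 17.9 |
| 12 | 50% | 48.8% | 33.3% | 15.5 |
| 15 | 25% | 61.2% | 33.3% | 27.9 |
| 15 | 36% | 60.5% | 39.1% | 21.4 |
| 15 | 50% | 60.9% | 41.9% | 19.0 |

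Repeat simulations agree to within about a point.

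**Loss by correlation** (both N, response rates 25% to 50%):

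| ρ | Loss (points) |
|---|---|
| 0.3 | 3 to 8 |
| 0.4 | 6 to 14 |
| 0.5 | 10 to 21 |
| 0.6 | 15 to 28 |
| 0.8 | 16 to 39 |

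**Sensitivity.**
- At a 77% response rate the loss is 18 to 42 points for ρ from 0.5 to 0.8.
- With the worst 20% to 35% of patients tied at a worst rank, ρ = 0.6, the gain from percent change is still 14 to 28 points.
- Against the ordinary logistic likelihood-ratio test at 36% response, with Pearson correlation on percent change, the apparent loss is −1 to 2 points at ρ = 0.3, 3 to 6 at 0.4, 7 to 12 at 0.5 and 14 to 19 at 0.6 to 0.7. That logistic test really rejects 7.5% to 8.3% of the time under no association, so part of its apparent power is excess false positives.

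**The case against.** The strongest reply is that these are exploratory analyses in a phase I safety trial that claims no power for them. Even on the better scale, power at ρ = 0.6 is about 49% (N = 12) to 61% (N = 15), for one marker at a time, with several markers and three IL-2 dose levels pooled. A null result would settle little on either scale. That stands, and it keeps the point small. It does not justify leaving measured information unused when using it is nearly free.

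The model also favours percent change. RECIST response depends on new and non-target lesions too, and a marker might act only at the response threshold. Both would shrink the gain, and neither is quantified here.

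A reader might infer three stronger things:
- **That the plan loses 15 to 28 points of power outright.** That range belongs to ρ = 0.6. The documents give no correlation, and at 0.3 the loss is single digits.
- **That every pretreatment marker is tied to yes/no response in 9.1.** TIL clonality has no stated outcome or model, and copy number is tied to ORR only in 4.2.4.3.5.
- **That depth of effect goes unanalysed.** Section 4.2.2 hypothesises that the combination "will result in a higher frequency and/or greater depth of anti-tumor effects in comparison to the historical experience" with monotherapy. This concerns the regimen, not the markers. Section 4.1.2 expresses depth as CR rate, and 9.1 lists CR and PR. Depth is analysed coarsely; only a continuous summary is missing.

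An argument that the responder analysis may give no result at all carries little weight. The chance that all or none respond at N = 12 is 0.77¹² + 0.23¹² = 4.3% at a 77% response rate and 0.75¹² + 0.25¹² = 3.2% at 25%.

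**Conclusion.** The point holds as an inexpensive improvement. The pretreatment markers named in 9.1 are related only to overall response, copy number is related to ORR in 4.2.4.3.5, and percent change derivable from scans already planned is not used. For weak associations the cost is a few points of power; for moderate to strong ones it is roughly 10 to 28 points at correlations of 0.5 to 0.6 and up to 39 at 0.8. These figures rest on the assumed correlation, response rates of 25% to 50%, size-valid rank tests, a two-sided 5% level without multiplicity adjustment, and response as an exact cut of percent change. The documents do not support a single figure for the loss. The safety objective and the ORR, DCR and PFS analyses are unaffected.

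**What to change.** In 9.1, add best percent change from baseline in the sum of RECIST 1.1 target-lesion diameters as an outcome for the pretreatment markers:
- For continuous markers (PD-L1, TIL density, T-cell and lymphocyte subsets, and TIL clonality, which now lacks a method), use Spearman correlation with a 95% interval.
- For each copy number alteration, present or absent, use an exact rank-sum test.
- Give the worst rank to patients whose best response is progression through new lesions or unequivocal non-target progression, and to those with no post-baseline scan because of progression or death.
- State in advance whether scans after first RECIST progression count toward the best change. Sections 4.2.4.2 and 5.7 allow a further course after it, so the answer affects the outcome.
- Keep CR/PR versus not as a companion analysis and define its coding.
- List each patient's best percent change, with the median by cohort and overall, as a descriptive supplement to CR, PR and ORR.

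The cost is SAP wording and a few lines of analysis, with no new patients, visits, scans or samples. The downsides are that percent change reflects new and non-target lesions only through the worst rank, is less familiar than the RECIST category, and has no historical figure in the documents to be compared with. Power stays modest, so the results should still be reported as exploratory.

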1.0 TRIAL SUMMARY

Abbreviated Title	IL-2 and Pembrolizumab for Advanced RCC
Trial Phase	Phase I
IND Number	133532
Clinical Indication	Advanced or metastatic clear cell RCC
Trial Type	Therapeutic
Type of control	Historical control
Route of administration	SQ IL-2; IV IL-2 IV pembrolizumab
Trial Blinding	None
Treatment Groups	Dose Level 1: SQ IL-2 plus IV pembrolizumab; Dose Levels 2 and 3: IV IL-2 plus IV pembrolizumab
Number of trial subjects	N=12 to 15
Estimated Enrollment Period	36 months
Estimated duration of trial	5 years
Duration of Participation	Maximum of 3 cycles of treatment (36 weeks) with follow-up.

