2.0 TRIAL DESIGN

2.1 Trial Design

This is a phase I, open-label, dose escalation and conditional cohort expansion at the maximum tolerated dose (MTD) of Interleukin-2 (IL-2; aldesleukin), a soluble cytokine growth factor for T lymphocytes, in combination with pembrolizumab (MK-3475), a humanized monoclonal antibody (mAb) of the IgG4/kappa isotype designed to target the Programmed Death 1 (PD1) membrane receptor on activated T lymphocytes. Treatment is for patients with advanced or metastatic clear cell renal cell carcinoma (RCC).

The study will consist of 3 periods: Screening (up to 28 days), Treatment (up to three 12-week courses), and Follow-Up (up to 1 year). Each treatment course (“course” nomenclature is by the conventions of IL-2 treatment) is comprised of 4 doses (cycles) of pembrolizumab given by iv infusion every 3 weeks combined with 1 cycle of IL-2 given by SQ administration daily 5 days/week for 6 weeks at Dose Level 1; or by IV bolus infusion (Dose Level 2 and 3) every 8 hours to a maximum of 14 doses on weeks 1 (cycle 1) and 4 (cycle 2) of a treatment course. Investigator tumor response assessment (by RECIST v1.1) must be completed before the first dose of the next treatment course. The maximum number of on-study treatment courses will be three.

Following completion of treatment, patients with ongoing disease control (CR, PR, or SD) will enter Surveillance Follow-Up. Disease status will be reassessed every 3 months for up to 1-year duration. Patients with disease control completing one year of Surveillance Follow-Up or patients with disease progression will enter Survival Follow-Up to study completion.

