Archival Tissue Collection / Tumor Biopsy / Correlative Studies																
Archival or Newly Obtained Tissue Collection		X ¹⁸														
Peripheral blood for T cell subset quantitation by flow cytometry		X ¹⁸						X					X		X	

Trial Period:	Study Screening	Treatment Courses ¹												Post-Treatment		
		1			2			3			4			Safety Follow-Up	Surveillance Follow-Up ²	Survival Follow-Up ³
Treatment Cycle/Title:		1	2	3	4	5	6	7	8	9	10	11	12			
Treatment Week		1	2	3	4	5	6	7	8	9	10	11	12			
Scheduling Window (Days):		-28 to -1	± 2	± 7	30 (± 7) days post EOT ⁴	Every 12 (± 1) week post EOT	Every 12 (± 1) week									
Peripheral blood for future correlative studies		X ¹⁸												X		X

¹Maximum duration of therapy is 3 courses.

²Post-treatment surveillance for patients with SD, PR, or CR.

³After PD, start of new cancer treatment, or completion of 1 year Surveillance Follow-Up

⁴EOT = end of treatment

⁵Dose Level 1 patients only. For each cycle day 1, administer IL-2 after pembrolizumab. Observe patients \geq 1 hour after the first pembrolizumab dose (day 1, cycle1) before administering the first SQ IL-2 dose.

⁶Dose Level 2 and 3 patients only. Patients will admit to begin IV IL-2 treatment on cycle day 2, (or next available ICU admission day).

⁷Evaluations for Dose Level 1 patients week 2,3,5,6 are only required during Course 1

⁸Evaluations for Dose Level 2 and 3 patients on week 2 and 5 follow hospital discharge for IL-2 cycles 1 and 2 respectively.

⁹Vital signs to include temperature, heart rate, respiratory rate, blood pressure, and pulse oximetry.

¹⁰A negative pregnancy test must be documented $<$ 72 hrs before each day 1 pembrolizumab dose for the start of each treatment course and at EOT. Pregnancy testing should be repeated whenever an expected menstrual cycle is missed or when pregnancy is otherwise suspected.

¹¹Screening serologies within 28 days of day 1

¹²Don't repeat labs cycle 1/day 1 if screening labs are $<$ 14 days old.

¹³Troponin-I testing prior to pembrolizumab cycle 3 and 4 required for course 1 only

¹⁴LVEF \geq 50% measured by MUGA scan, echo, or stress test study with myocardial perfusion imaging. A cardiac study documenting LVEF \geq 50% (MUGA, echo, or stress testing) obtained prior to study enrollment and within 6 months of study day 1 is acceptable screening and does not need to be repeated.

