7.2.5.2 Surveillance Follow-Up Visits

Subjects who complete or discontinue trial treatment with a disease status of CR, PR or SD will move into the Surveillance Follow-Up Phase and should be assessed every 12 weeks (84 ± 7 days) by radiologic imaging to monitor disease status. Every effort should be made to collect information regarding disease status until the start of new anti-neoplastic therapy, disease progression, death, or end of the study. Information regarding post-study anti-neoplastic treatment will be collected if new treatment is initiated.

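### Two exploratory analyses in Section 9.1 need correcting: end-of-treatment tumour has no scheduled collection, and the Cox model's PFS clock is not tied to its end-of-treatment population

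*Combined protocol and SAP*

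**What the plan says.** **PFS and the Cox model (Section 9.1).** PFS has one definition: "Progression-free survival will be defined from the time of registration to progression or death". The blood analysis uses an "end of cycle peripheral blood re-analysis to quantify lymphocyte subsets", and its association with PFS "will be evaluated using a Cox proportional hazards model, among patients alive and progression-free at end of treatment". The sentence names no other time origin. The next sentence extends the approach to PD-L1, TIL density and T-cell subsets in tumour at the end of treatment, in patients without a CR who are still progression-free.

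**Length of treatment.** Section 2.1 gives the periods as "Treatment (up to three 12-week courses), and Follow-Up (up to 1 year". Section 7.2.5.2 adds: "Subjects who complete or discontinue trial treatment with a disease status of CR, PR or SD will move into the Surveillance Follow-Up Phase".

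**Meaning of cycle.** In Section 2.1 a course contains "4 doses (cycles) of pembrolizumab given by iv infusion every 3 weeks", and the same section also counts IL-2 in cycles. Section 1.0 has "Maximum of 3 cycles of treatment (36 weeks) with follow-up", where a cycle must be a 12-week course.

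**Samples (Section 6.1).** The row "Peripheral blood for T cell subset quantitation by flow cytometry" shows a pre-treatment draw, draws near weeks 7 and 12 of a course (as far as the extracted columns can be read) and a post-treatment draw. The tissue row has one mark, which footnote 18 ties to before C1D1. Section 7.2.2.6 refers to the flow chart for all correlative blood and tissue.

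**The concern.** The first problem is that an analysis is listed for which no sample is scheduled. Section 4.2.4.3.2 deepens the conflict: it expects TIL to be assessed during therapy as well as at baseline, whereas the PD-L1 objective in Section 3.3 names pretreatment tumour only.

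The second is guaranteed event-free time. A patient enters the Cox model only if progression-free at end of treatment, so none can have an event before that date. If time nevertheless runs from registration, a three-course patient sits in the risk set between weeks 12 and 36 with no possibility of an event, while a one-course patient can fail. A marker that merely changes with the number of courses can then look protective or harmful.

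At stake is the reading of exploratory biomarker results that Section 3.0 says will inform future studies. No safety decision depends on them.

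**Working it through.** The plan gives no alpha, effect size or event count for these analyses, so there is no figure to reproduce.

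**1. Tissue: the sections side by side**

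| Section | What it implies for tumour after C1D1 |
|---|---|
| 9.1 | Required at end of treatment in non-CR patients |
| 4.2.4.3.2 | TIL assessed during therapy |
| 3.3 | PD-L1 from pretreatment tumour |
| 6.1, footnote 18 | One collection, before C1D1 |
| 7.2.2.6 | Flow chart governs |
| 7.2 | Unscheduled procedures only if clinically necessary |

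Scheduled end-of-treatment tumour collections: none. A shifted column in the extracted table would not change this, because the footnote fixes the timing of the single mark.

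**2. Clock: why the score is off centre**

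From the documents: up to 3 courses × 12 weeks = 36 weeks, so end of treatment falls at about week 12, 24 or 36. Assumed: equal thirds with 1, 2 and 3 courses; marker = N(0,1) + 0.5 × courses; no true effect.

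- Mean marker by course count: 0.5, 1.0, 1.5; overall (0.5 + 1.0 + 1.5)/3 = 1.0.
- Any event between weeks 12 and 24 must be in a one-course patient, with expected marker 0.5.
- Registration clock: the risk set just after week 12 is everyone, mean 1.0. Expected score contribution is 0.5 − 1.0 = −0.5, which pulls the HR below 1.
- Delayed entry: the risk set is one-course patients only, mean 0.5. Contribution is 0.5 − 0.5 = 0.

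**3. Clock: size by simulation**

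Settings, all assumed: exponential time from end of treatment with median 4 or 8 months, censored 52 weeks after it; 16 runs of 1,200 patients per cell; exponentiated mean log HR per SD; Monte Carlo error about 0.01. True HR is 1.00. Entries are the registration clock at 4 / 8 months.

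| Courses 1/2/3 | −0.5 SD per course | 0 | +0.5 SD | +1.0 SD |
|---|---|---|---|---|
| equal thirds | 1.14 / 1.10 | 0.99 / 1.01 | 0.87 / 0.92 | 0.82 / 0.86 |
| 50/25/25% | 1.14 / 1.08 | 1.00 / 1.00 | 0.87 / 0.90 | 0.83 / 0.86 |
| 10/10/80% | 1.08 / 1.06 | 1.00 / 1.00 | 0.92 / 0.96 | 0.88 / 0.89 |

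Repeating the simulation puts the lower end between 0.82 and 0.84. Delayed entry, or an end-of-treatment origin, gave 0.97 to 1.02 in every cell. With all patients on three courses the clocks gave identical results. With a marker unrelated to course count the null is unbiased, though a true HR of 0.50 reads as 0.51 to 0.54.

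**4. Against sampling error**

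With 8 or 12 patients in the set and 5 to 11 events, the 95% interval is about ×/÷ 1.8 to 3.2. The largest shift in the table, 1/0.82 = ×/÷ 1.22, is well inside it.

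**5. Is end of treatment a defined date?**

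Section 6.1 only expands the abbreviation and places the safety visit 30 days after end of treatment. Section 7.2.5.1 places the same visit 30 days after the last dose. The last pembrolizumab dose of a course is in week 10 and the restaging scan is at the end of the course. If end of treatment means last dose, the week-12 draw and scan come after it.

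**The case against.** **The origin is unstated, not wrongly stated.** Restricting to patients progression-free at end of treatment is what a landmark analysis does, and the author may have meant to restart the clock there. A reader might infer that the plan prescribes a biased analysis. The documents do not support that: registration is the default because it is the only origin given. The need to state the origin stands.

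**The bias needs a marker–course link that no section quantifies.** Section 4.2.4.3.2 says Tregs expand under IL-2, which makes a link plausible, but 0.5 to 1.0 SD per course is an assumption. If the intended draw is a fixed early one, such as the end of course 1, later drift cannot enter it and the unrelated case may be the right one. This objection stands, and it is a further reason to name the draw.

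**The assumed sizes fit loosely.** If a 4-month median also held on treatment, the progression-free fractions at weeks 12, 24 and 36 would be about 0.62, 0.38 and 0.24. They average 0.41, so about 5 to 6 of 12 to 15 patients would enter the model. At 8 months the average is 0.63, or about 8 to 9 patients, and the shifts are the smaller ones in the table. This also stands.

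**The tissue gap may be a missing flow-chart mark.** The flow-chart section heading mentions tumour biopsy, and limiting the analysis to non-CR patients fits sampling of residual tumour. A reader might infer that the analysis is simply impossible, but the documents do not show which side is the mistake. They show only that the two sides conflict.

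**Conclusion.** Both points hold, and both are confined to exploratory objectives. The tissue conflict needs no assumptions: Section 9.1 analyses a sample that the governing schedule does not collect.

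The clock point is conditional. On the default registration origin, a marker that rises by 0.5 to 1.0 SD per course gives a null HR of about 0.82 to 0.96 in large samples under the course mixes tried; at −0.5 SD per course it gives about 1.06 to 1.14. Null bias is essentially nil if the marker is unrelated to course count, and absent if everyone ends treatment at the same time. The shift is systematic but smaller than the sampling error in this trial, so it should not be read as making the results misleading on its own. The tumour analysis, if kept at end of treatment, has the same clock problem.

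A reader might go further and expect the logistic response models to break down at this sample size. That depends on dichotomising PD-L1 or entering several markers jointly. The plan states neither, so the point is not made here.

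**What to change.** **Tissue.** Reconcile Sections 4.2.4.3.2, 6.1, 7.2.2.6 and 9.1 on whether any tumour is collected after C1D1. If none is, drop the end-of-treatment tumour analysis, or restate it on pre-treatment tissue with PFS from registration in all patients. If later tissue is already intended, show it in the flow chart and apply the clock below.

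**Clock.** In Section 9.1:

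- define the end-of-treatment date, as last dose or end-of-course assessment, and align Sections 6.1 and 7.2.5.1 with it;
- name the blood draw by course and week in place of end of cycle;
- start PFS at the later of that draw and the end-of-treatment assessment, among patients progression-free then, or keep registration as origin with delayed entry at that date.

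**Cost.** This is SAP wording and standard software, plus a flow-chart entry if later tissue is intended. One listed analysis may be dropped. Delayed entry widens the interval slightly: from ×/÷ 1.98 to 2.07 with 12 patients and from 2.56 to 2.81 with 8 (equal thirds, +0.5 SD, 4-month median). Restarting the clock at end of treatment does not widen it (1.95 and 2.51).
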